Specific Aim 1: Test the hypothesis that clopidogrel monotherapy is safe following successful PCI among 100 consecutive patients with HBR and meeting the inclusion criteria (100 *active* patients, excluding patients who have been enrolled then withdrawn for various reasons such as starting an additional blood thinner, patient preference, etc.). To ensure that we have data on 100 active patients that complete their 1 month visit, we will plan to accrue up to 150 patients. The primary safety end point will be showing noninferiority of clopidogrel monotherapy in reducing ischemic events stratified by presence or absence of *CYP2C19* LOF allele (QuantStudio with Chemagic DNA extraction). All patients will receive clopidogrel (600 mg load & 75 mg maintenance) and aspirin (324 mg load & 81 mg maintenance) for the first week. Those with *CYP2C19* 2* or 3* LOF allele (*CYP2C19* LOF carriers) will be prescribed prasugrel or ticagrelor [prasugrel 60 mg load, maintenance 10 mg or 5 mg (for patients \geq 75 years or $<$ 60 kg) daily or ticagrelor 180 mg load, maintenance 90 mg twice daily (dose escalation with bolus will occur regardless of the timing of the last clopidogrel dose)]. Non-carriers (or those with inconclusive results) will continue with clopidogrel 75 mg daily maintenance dose. Aspirin will be stopped in all patients once *CYP2C19* results are available.

Specific Aim 2: Among participants enrolled in aim 1, aim 2 will determine the incidence of BARC 3 or 5 bleeding events. Other secondary endpoints are post-dismissal all-cause death, any MI up to 180 days, repeat revascularization, or any other BARC bleeding episodes.

SIGNIFICANCE

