| Spontaneous bleeding requiring hospitalization or transfusion in the past 6 months or at any time, if recurrent | Spontaneous bleeding requiring hospitalization or transfusion within the past 12 months not meeting the major criterion |
| Moderate or severe thrombocytopenia (platelet count $<100 \times 10^9/L$) present prior to PCI | |
| Chronic bleeding diathesis | |
| Liver cirrhosis with portal hypertension | |
| Recent major surgery or major trauma within 30 days before PCI | Long-term use of oral nonsteroidal antiinflammatory drugs (NSAIDs) or steroids |
| Active malignancy (excluding nonmelanoma skin cancer) within the past 12 months | |
| Previous spontaneous intracranial hemorrhage (at any time) | Any ischemic stroke at any time not meeting the major criterion |
| Previous traumatic intracranial hemorrhage within the past 12 months | |
| Presence of a bleeding arteriovenous malformation | |
| Moderate or severe ischemic stroke within the past 6 months | |
| Nondearable major surgery on DAPT | |

Table 2: Percent of Patients with Death or Myocardial Infarction After PCI

| Year | 30 days | 60 days | 90 days |
|--------|---------|---------|---------|
| 2010 | 14% | 16% | 17% |
| 2011 | 17% | 20% | 22% |
| 2012 | 10% | 11% | 13% |
| 2013 | 9% | 11% | 13% |
| 2014 | 6% | 8% | 8% |
| 2015 | 6% | 8% | 9% |
| 2016 | 5% | 6% | 7% |
| 2017 | 5% | 6% | 6% |
| Total* | 9% | 11% | 12% |

*MI data unavailable after 2017; Data from Mayo Clinic, Rochester, MI, myocardial infarction

clinical trials, including genotype-directed randomization for the TAILOR PCI trial. We will approach potential participants for informed consent before dismissal following the PCI procedure. For participant with same-day dismissal, we will approach them either before coronary angiography or pre-dismissal once the sedation from the procedure wears off.

Aim 2: Detailed Approach

Aim 2 includes participants enrolled in Aim 1, and this data will determine the incidence of post-discharge BARC 3 or 5 bleeding events. Other secondary endpoints are post-dismissal all-cause death, any MI up to 180 days, repeat revascularization, or any other BARC bleeding episodes. The rate of death or MI post-PCI at Mayo Clinic, Rochester is presented in **Table 2**.

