Background. Recent randomized trials have investigated different antithrombotic strategies, including monotherapy with a P2Y₁₂ inhibitor, aiming to assess the best balance between ischemic and bleeding risks after PCI. Shortening of DAPT duration is safe and has not demonstrated an increase in the incidence of ischemic risk. The limitations of the existing trials are, 1) that DAPT is given for 1-3 months, and there is an urgent need aspirin-free P2Y12 inhibition in the first month following PCI that overlaps with high risk period for PDB, 2) TWILIGHT trial randomized higher-risk patients only after demonstrating no ischemia or bleeding for the initial 3 months following PCI thereby selecting lower-risk patients for PDB, 3) ASET pilot study included only low-risk, stable patients who were given prasugrel. Older age is one of the main drivers of bleeding and along with prior TIA/stroke, or low body weight will significantly limit the applicability of monotherapy with prasugrel. In that regard, individualizing P2Y12 therapy guided by genotyping at the time of PCI allows us to use clopidogrel with lower attendant bleeding risk among non-carriers (prevalence of 60%-70%) and limiting the use of newer P2Y12 inhibitors to the rest. Accurate assessment and prolongation of period of observation is relevant especially among participants presenting with ACS.

The central goal of Aim 2 is to study the incidence of PDB and ischemia during the first 6 months following PCI with DES.

This aim leverages the support from existing Mayo Clinic PCI database in whom all the information is routinely collected following a coronary intervention.

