Preliminary Studies. Research Design: Same 150 participants from Aim 1 will be enrolled, however, data for Aim 2 will be collected at six months. Our main strategy for this aim is to demonstrate whether clopidogrel monotherapy, guided by genotype, is associated with lower bleeding and ischemic events during extended period of observation, especially relevant in participants presenting with ACS. **Expected Outcomes:** Upon completion, we will have comprehensive data on incidence, severity, predictors, type, and time trends for both PDB and ischemia. In recent years, several trials have analyzed PCI in HBR patients examining DAPT regimens and outcomes to balance the risk of ischemia and bleeding. **Table 3** (see supplemental material) summarizes these key trials. Extending the period of observation allows us to monitor the participants longer and demonstrate the safety of clopidogrel monotherapy. From this aim we will determine whether clopidogrel monotherapy is safe in all-comers following successful PCI, especially among participants presenting with ACS, as the current guidelines recommend at least 6 months of DAPT. Importantly, with this aim, we will focus on the period between 3 and 6 months for both ischemic and bleeding events. The idea is that by providing early deescalation with a P2Y12 inhibitor, clopidogrel will lead to lowering in the incidence of PDB. The observation period will continue even beyond 6 months as all participants will be entered into the Mayo Clinic database. We expect that subjects receiving clopidogrel monotherapy will have reduced PDB during 6 months of observation. If the data confirm our hypotheses, we will expect our hypothesis and will have shown after completion of Aim 2 that clopidogrel monotherapy is safe and effective during 6 months of observation.

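### The protocol does not show that the PCI database supporting Aim 2 captures MI, and no participant contact is scheduled after about Day 90, so the 180-day MI rate is likely to be biased low

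*Combined protocol and SAP*

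**What the plan says.** **The endpoint.** Specific Aim 2, and again Aim 2: Detailed Approach, list among the secondary endpoints "post-dismissal all-cause death, any MI up to 180 days". The Design Overview also sets the Aim 2 assessment at up to 180 days. The Aim 2 research design adds that "we will focus on the period between 3 and 6 months for both ischemic and bleeding events".

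**The source.** The Aim 2 Background says: "This aim leverages the support from existing Mayo Clinic PCI database in whom all the information is routinely collected following a coronary intervention". The Aim 2 research design says "data for Aim 2 will be collected at six months", without saying by what means. For later follow-up it says: "The observation period will continue even beyond 6 months as all participants will be entered into the Mayo Clinic database".

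**What the protocol says about its own MI data.** The footnote to Table 2, which gives death or MI after PCI by year from 2010 to 2017, reads "MI data unavailable after 2017; Data from Mayo Clinic, Rochester". The Potential Problems paragraph of Aim 2 accepts that routine capture may miss bleeding and ischemic events treated at outside facilities. It offers a surveillance programme that contacts participants and obtains their records.

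**Scheduled contact.** General Methods item 3 has the coordinator assess events at discharge, 1 month and 3 months, with medical record review if telephone contact fails. Item 4 sets trial duration at 90 days. Items 6c and 6d repeat the 1- and 3-month calls. The last column of the Schedule of Events is Day 90 ± 1 week.

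**The concern.** The statement that the database collects everything is hard to square with a footnote in the same protocol saying that MI data stop at 2017. Nothing in the text reconciles the two. On its own this would be a wording problem. It becomes a measurement problem because the database is the support named for Aim 2, and Aim 2 concentrates on an interval in which no one is scheduled to speak to the participant.

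If MI between Day 90 and Day 180 is found only when a record happens to reach the study team, missed events will look like event-free follow-up. The 6-month MI rate would then be too low. In a single-arm study meant to show that very early aspirin withdrawal is safe, that error is in the reassuring direction. Item 3 also counts only adjudicated events, so an MI without source records drops out of the analysis.

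**Working it through.** **1. Reproduce the figure that carries the footnote.** Yearly denominators are not given, so I took unweighted means of the eight rows of Table 2 (2010 to 2017):
- 30 days: (14+17+10+9+6+6+5+5)/8 = 72/8 = 9.0%; stated 9%.
- 60 days: (16+20+11+11+8+8+6+6)/8 = 86/8 = 10.75%; stated 11%.
- 90 days: (17+22+13+13+8+9+7+6)/8 = 95/8 = 11.875%; stated 12%.

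The total row reproduces and is consistent with covering 2010 to 2017 only. The table stops at 90 days, so it gives no 180-day figure, and it does not split death from MI.

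**2. Does the protocol show that the database holds current MI data?** Set side by side:
- For: the Aim 2 Background sentence.
- Against: the Table 2 footnote and the out-of-network caveat.
- Suggestive: Aim 1 Preliminary Studies reports high-bleeding-risk prevalence in the same catheterization laboratory from January 2010 to July 2021, about 3.5 years past the last MI year in Table 2. Local PCI data therefore ran on after the MI series ended. That fits MI follow-up being missing, late or not extracted, and does not say which.
- Also relevant: item 7 (Control Cohort) uses the registry to find patients but takes events from ICD codes verified by chart review.

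Completeness for MI is asserted in one place and put in doubt in others.

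**3. How much of the endpoint window has no scheduled contact?** Counting from PCI, the last call falls between Day 83 and Day 97 (90 ± 7). That leaves 180 − 97 = 83 to 180 − 83 = 97 days uncovered, or 83/180 = 46% to 97/180 = 54% of the window. Record review under item 3 is triggered by a failed call, and after Day 90 there is no call to fail. The surveillance programme has no stated time point and no line in the Schedule of Events.

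**4. How many events might be at stake?** This is an illustration, because the documents give no rate for months 3 to 6.
- Table 2 increments from day 60 to day 90: 2016, 7 − 6 = 1 point; 2017, 6 − 6 = 0; mean 0.5. Over 2010 to 2017: (1+2+2+2+0+1+1+0)/8 = 9/8 = 1.125 points.
- Assumed range for death or MI in months 3 to 6: 0.5% to 3%. The lower end equals one recent 30-day increment. The upper end is close to three 30-day blocks at the long-run average (3 × 1.125 = 3.4%).
- Expected events = n × rate. For n = 100: 0.5 to 3. For n = 150: 0.75 to 4.5.
- Chance of at least one event = 1 − (1 − rate)^n: from 39% (n = 100, 0.5%) to 99% (n = 150, 3%).

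The increments come from rounded percentages, and the table does not say that it is limited to high-bleeding-risk patients, so the range is rough. The MI share is unknown.

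**5. Why a small count matters.** With 0 events in 100, the exact two-sided 95% upper limit is 1 − 0.025^(1/100) = 3.6%. With 2 in 100 the exact (Clopper–Pearson) upper limit is 7.0%. Missing two events would roughly halve the upper limit reported.

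**The case against.** The strongest reply is that the footnote proves little. It describes a historical table, gives its source only as the institution, does not name the PCI database, and does not say whether MI recording stopped or later years were simply not extracted or linked. A reader might infer that the database cannot supply the MI endpoint, or that every MI after Day 90 would be recorded as zero. The documents support neither. The Aim 2 Background says only that the aim draws support from the database, not that it is the sole source. The plan also describes prospective collection at six months, medical record review, adjudication, and a programme to contact participants and retrieve records. The available text of that last paragraph breaks off in mid-list, so its silence should not be held against the plan. The sentence that rests on database entry alone concerns observation beyond 6 months, where no endpoint is defined.

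A reader might also infer that controls lack an MI source. They do not: item 7 specifies ICD codes with a myocardial infarction category, verified by chart review, in patients treated within the last 2 years.

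Finally, it can be said that this is just a missing Day 180 visit. The remedy does overlap. But the database sentence is what could make such a visit seem unnecessary, and the protocol's own text undercuts it.

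What does not stand is the suggestion that the other sources close the gap as written. Neither record review nor the surveillance programme is tied to the period from Day 90 to Day 180.

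**Conclusion.** The point holds in a limited form. The protocol does not show that the PCI database captures MI after PCI, and it schedules no participant contact for roughly the second half of the 180-day window that Aim 2 says it will focus on. Followed as written, MI in that interval is likely to be under-counted and the 6-month rate biased low.

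The size cannot be derived from the documents. Under the assumed 0.5% to 3% for death or MI in months 3 to 6, about 0.5 to 4.5 events are expected in 100 to 150 patients. Only the MI part, and only the part that other sources miss, would be lost. The conclusion rests on reading the footnote as leaving database completeness for MI unproven, and on the schedule of events being the full list of planned contacts. The primary composite is not affected by this point, since its windows close at 30 and 90 days.

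**What to change.** - In the Aim 2 Background, strike or qualify the statement that the database routinely collects everything. Under Table 2, say why MI data end in 2017: not collected, not extracted or not linked.
- Add a Day 180 coordinator contact to the Schedule of Events for every participant, with medical record review and retrieval of outside records whether or not the call succeeds. Send every suspected MI to the adjudication committee. Bring the stated 90-day trial duration into line with this.
- State that MI in participants will not be taken from the PCI database alone, and limit database-only follow-up beyond 6 months to outcomes the database is shown to capture.
- Leave control MI ascertainment as it is.

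The cost is a few lines of protocol text and one further call, with record retrieval, for each of up to 150 participants. Coordinator calls, record retrieval and adjudication are already in the plan, so the added coordinator time is modest.

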5. **Definitions and Role of Data and Safety Monitoring Board (DSMB):** All deaths will be considered cardiac unless a clear noncardiac cause can be ascertained. Spontaneous MI will be defined according to the fourth universal definition.²¹ Periprocedural MI (< 48 hours post-PCI) will be defined according to the 2013 definition of the Society for Cardiovascular Angiography and Interventions.²² Stent thrombosis will be defined and classified according to the Academic Research Consortium-2 definition.²³ BARC bleeding will be defined as previously reported.²⁴ All endpoints will be independently adjudicated by the clinical event committee. An independent DSMB will oversee the individual and collective safety of the patients in the study during enrollment and follow-up. To provide the steering committee with timely feedback on potential safety issues, the DSMB will review the data 3 times during the trial: (1) When the 25th patient is enrolled, (2) when the 50th patient is enrolled, (3) when the 100th patient is enrolled, and (4) when the 100th actively enrolled patient completes 1-month follow-up.
6. **Subjects**
 - a) **Inclusion Criteria:** Informed consent after successful PCI [no non-fatal MI/stroke/repeat target revascularization/bleeding/acute kidney injury] and academic research consortium-high bleeding risk (ARC-HBR) score ≥ 4 .
 - b) **Exclusion Criteria:** Chronic use of warfarin or direct oral anticoagulant (DOAC), unsuccessful PCI (see above), lesions with angiographic thrombus, prior PCI within 6 months (except for staged PCIs within the same hospitalization or within 7 days of initial PCI, in which case enrollment will occur following the final planned/staged PCI), planned PCI greater than 7 days but less than 6 months following index PCI, planned surgical intervention to treat any cardiac or noncardiac condition within 6 months (excluding transcutaneous valve interventions and pacemakers), high risk lesion/stent characteristics (>50% unprotected left main disease, bifurcation disease requiring 2 stents technique, rotational atherectomy, vein graft, unprotected left main intervention, or history of definite stent thrombosis), women of child-bearing age unless negative pregnancy test is done, life expectancy <1 year, known drug/alcohol dependence, and assessment that the patient will not be compliant with the study protocol.

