- Hemoglobin at time of bleeding event (obtain from chart review; not available in registry)
- Creatinine and eGFR at time of PCI
- Use of clopidogrel, prasugrel, ticagrelor
- Use of oral anticoagulant (warfarin, apixaban, rivaroxaban)

Aim 1: Detailed Approach

The objective of aim 1 is to determine if clopidogrel monotherapy following successful PCI is safe among non-carriers of CYP2C19 LOF allele. The hypothesis is that carriers of CYP2C19 LOF genotype are unable to metabolize clopidogrel effectively to an active drug that blocks P2Y12 receptors and inhibit platelet aggregation and are therefore at heightened ischemic risk following PCI. We will reduce bleeding risk by giving clopidogrel monotherapy only to non-carriers. Our approach to test this hypothesis is stratifying HBR patients after successful PCI into those with CYP2C19 LOF allele and those with inconclusive results or who are

| Schedule of Events | Day 0 | Day 1 | Day 2 | Day 3 | Day 4 | Day 5 | Day 6 | Day 7 ± 2 days | Day 30 ± 1 week | Day 90 ± 1 week |
|--|-------|-------|------------|-------|-------|-------|-------|-------------------|--------------------|--------------------|
| Stent Placement | ■ | | | | | | | | | |
| Informed Consent | | ■■■ | | | | | | | | |
| Genotype Test Blood Draw | | ■■■■ | | | | | | | | |
| Study Coordinator Call with Genotype Results & Final Medication Decision | | | ■■■■■ | | | | | | | |
| Stop aspirin and continue clopidogrel or change to prasugrel/ticagrelor | | | ■■■■■■■■■■ | | | | | | | |
| 1 st Study Coordinator Follow Up Call | | | | | | | | ■ | | |
| 2 nd Study Coordinator Follow Up Call | | | | | | | | | ■ | |
| 3 rd Study Coordinator Follow Up Call | | | | | | | | | | ■ |

non-carriers. Within first week of DAPT initiation, non-carriers will receive clopidogrel monotherapy, and prasugrel/ticagrelor will be given to patients with CYP2C19 LOF allele. The *rationale* for this aim is to individualize antiplatelet therapy and to reduce bleeding risk by stratifying P2Y12 pharmacotherapy by the CYP2C19 LOF genotype. Large number (50%-70%) of patients are non-carriers and in them clopidogrel monotherapy would suffice and the remainder will receive prasugrel or ticagrelor thereby lowering bleeding risk, cost, and unique adverse effects related to ticagrelor (e.g., bradycardia, dyspnea) or excess bleeding related to prasugrel. Recruitment should not be a challenge at Mayo Clinic, Rochester where 30% of PCI patients are HBR.

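### Aim 2 states its safety conclusion for all-comers and especially ACS, but the design supports one only for eligible high-bleeding-risk patients who stay on clopidogrel, with ACS results descriptive

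*Combined protocol and SAP*

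**What the plan says.** Aim 2, Expected Outcomes, sets the target: "we will determine whether clopidogrel monotherapy is safe in all-comers following successful PCI, especially among participants presenting with ACS". The same section closes by saying that, if the hypotheses are confirmed, the investigators "will have shown after completion of Aim 2 that clopidogrel monotherapy is safe and effective during 6 months of observation".

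Aim 2 enrols nobody new. Its Research Design says "Same 150 participants from Aim 1 will be enrolled". Those participants are restricted in General Methods, item 6 (Subjects):

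- Inclusion requires "academic research consortium-high bleeding risk (ARC-HBR) score ≥ 4".
- The exclusions begin with "Chronic use of warfarin or direct oral anticoagulant (DOAC), unsuccessful PCI (see above), lesions with angiographic thrombus". They go on to unprotected left main disease or intervention, bifurcations needing two stents, rotational atherectomy, vein grafts and a previous definite stent thrombosis, among others.

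General Methods, item 2, assigns treatment after the genotype result. Non-carriers and patients with an inconclusive result stay on clopidogrel alone; carriers of a loss-of-function allele move to prasugrel or ticagrelor alone.

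Elsewhere the scope is stated more narrowly. Specific Aim 1 tests whether "clopidogrel monotherapy is safe following successful PCI among 100 consecutive patients with HBR and meeting the inclusion criteria". Aim 1: Detailed Approach says "The objective of aim 1 is to determine if clopidogrel monotherapy following successful PCI is safe among non-carriers".

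**The concern.** The Aim 2 sentence names a population (everyone after successful PCI), a treatment (clopidogrel monotherapy) and a subgroup of special interest (ACS). The population is wider than the one enrolled. The treatment is not the one every participant receives. For the subgroup, the plan gives no number, stratum or analysis.

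At stake is what the final report may claim. A favourable result could be reported, in line with the plan, as evidence of safety in patients without high bleeding risk, in confirmed carriers, or in patients with the lesion types that were kept out. None of these contributes data on clopidogrel monotherapy. For ACS the problem is different: such patients can enter, but too few are likely to be on clopidogrel monotherapy for the word *determine* to be justified.

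**Working it through.** The documents state no sample-size calculation, margin or error rate for this claim, so there is no figure of theirs to reproduce. The check has two parts.

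**1. Scope: the claim against the design**

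| Element of the claim | What the design provides |
|---|---|
| All-comers after PCI | ARC-HBR score of at least 4; no chronic warfarin or DOAC; no angiographic thrombus; none of the listed lesion or stent features |
| Clopidogrel monotherapy | Non-carriers and inconclusive genotypes only |
| Especially ACS | ACS eligible (Significance section), but no ACS count, stratum or analysis |

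The size of the gap can be gauged from the protocol's own figures. Aim 1: Detailed Approach describes the site as one "where 30% of PCI patients are HBR" and gives 50% to 70% as the non-carrier share. If genotype is unrelated to bleeding risk (assumption):

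- 0.30 × 0.50 = 15% of local PCI patients
- 0.30 × 0.70 = 21% of local PCI patients

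So roughly 15% to 21% of local PCI patients are HBR non-carriers, before the lesion and anticoagulant exclusions are applied. Inconclusive genotypes would add to this; their share is not given.

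**2. Precision: how many patients inform the ACS statement**

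Inputs:

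- Total N: 100 active patients, with accrual of up to 150 (Specific Aim 1); Aim 2 refers to 150.
- Non-carrier share: 50% to 70% (Aim 1: Detailed Approach). The Aim 2 Background gives 60% to 70%; the wider range is used here.
- ACS share: not in the documents; 30% to 70% is assumed, the same in carriers and non-carriers.

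Formulas: n = N × non-carrier share × ACS share. With zero events in n patients, the exact one-sided 95% upper limit is 1 − 0.05^(1/n).

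| N | Non-carriers | ACS (assumed) | n | Upper limit with 0 events |
|---|---|---|---|---|
| 100 | 50% | 30% | 15 | 18.1% |
| 100 | 50% | 50% | 25 | 11.3% |
| 100 | 70% | 50% | 35 | 8.2% |
| 100 | 70% | 70% | 49 | 5.9% |
| 150 | 50% | 30% | 22.5, taken as 22 | 12.7% |
| 150 | 70% | 70% | 73.5, taken as 74 | 4.0% |

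Zero events is the most favourable result possible. If events occurred at about 6% (the 2017 90-day death or MI rate in Table 2, used only for illustration), the two-sided exact 95% intervals would be about 0.2% to 32% for 1 of 15 and 1.5% to 13.3% for 4 of 74.

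For all clopidogrel monotherapy patients, ACS or not, N = 100 gives n = 50 to 70 and N = 150 gives n = 75 to 105. The zero-event one-sided limits are 5.8% to 4.2% and 3.9% to 2.8%.

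**The case against.** The strongest reply is that this is one loose phrase in narrative text. Specific Aim 1, the Aim 1 objective and the Aim 1 Expected Outcomes all state the scope correctly. Aim 2 itself says that the participants are those of Aim 1 and that treatment is guided by genotype, and the study is described as a pilot. No enrolment rule or endpoint depends on the phrase. All of that is true, and it is why the remedy is small. But the phrase stands in the section that says what Aim 2 will establish, and correct wording elsewhere does not withdraw it.

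A charitable reading is that *all-comers* means stable disease plus ACS, in contrast with the earlier prasugrel pilot that took only stable patients. The text does not say so, and the lesion and genotype restrictions would still conflict with it.

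The objection does rule out several stronger inferences that a reader might draw:

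- *The plan promises that clopidogrel monotherapy is safe.* It does not. The main sentence says it will determine whether this is so, and the closing sentence is conditional on the hypotheses being confirmed.
- *Carriers never receive clopidogrel.* Everyone receives clopidogrel with aspirin until the genotype result. Carriers do not receive clopidogrel monotherapy.
- *The thrombus exclusion removes most ACS patients, or ACS is the smaller subgroup.* The exclusion narrows which ACS patients can enter, but the documents give neither the loss nor an ACS count.
- *Even zero events could not exclude the 5% death or MI rate in Table 2.* This depends on the assumed ACS share and on N: at N = 150 with 70% non-carriers and 70% ACS, the limit is 4.0%. The 5% is also a 30-day rate for 2016 and 2017, not identified as ACS or HBR, while Aim 2 runs to six months.

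**Conclusion.** The concern holds as a mismatch between the stated Aim 2 conclusion and the design. The trial can inform the safety of clopidogrel monotherapy in eligible HBR patients who are non-carriers or have an inconclusive genotype. It cannot inform it in all-comers. This part rests on the protocol's text alone.

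For ACS, about 15 to 49 clopidogrel patients of 100, or about 22 to 74 of 150, would carry the statement, with zero-event upper limits of about 18% to 6% or about 13% to 4%. These figures rest on the assumed 30% to 70% ACS share and the protocol's 50% to 70% non-carrier share; they leave out inconclusive genotypes, which would raise n somewhat. Across the range, the data can describe ACS outcomes but are too imprecise to determine safety. The conclusion does not depend on a comparison with Table 2. Enrolment, treatment and sample size are not called into question by this point.

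**What to change.** 1. In Aim 2, Expected Outcomes, replace *all-comers* with: eligible HBR patients who are CYP2C19 non-carriers or have an inconclusive genotype and continue on clopidogrel monotherapy. Include the inconclusive group explicitly, because those patients also stay on clopidogrel.
2. Apply the same limit to the closing sentence on safety and effectiveness over six months.
3. Add a planned table giving ACS and non-ACS participants separately, with the number at risk, event counts and exact confidence intervals. The control cohort (General Methods, item 7) already records STEMI, NSTEMI or unstable angina, and chronic disease, so the same categories can be used for participants.
4. State that the ACS results are descriptive.

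The cost is a narrower stated claim and a small added tabulation.
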